#### **9.2.1 Study Period**

The study enrollment period will start in May 2018, when erenumab-aooe was approved in the U.S. and continue through November 2027. Descriptive interim analyses will be conducted annually, CCI

The final report will be delivered in November 2028. Due to a three to nine-month lag in data availability from administrative claims databases and the planned end of data collection, the final study report will cover the time period from May 2018 through November 2027.

## 9.2.2 Subject/Patient/Healthcare Professional Eligibility

### 9.2.2.1 Inclusion Criteria

Two cohorts of patients will be followed for outcomes:

- 1) Pregnant women with migraine
- 2) Live-born infants of pregnant women with migraine

Inclusion criteria for the cohort of pregnant women with migraine are as follows:

- 1) Women who are pregnant and ages 16-44 years of age at estimated LMP date. Pregnancy will be defined using combinations of ICD-10-CM diagnosis codes and CPT procedure codes, which includes having evidence of at least one of the following pregnancy outcomes: spontaneous abortion, stillbirth, live birth, therapeutic abortion, or ectopic pregnancy.
- 2) Have evidence of migraine during the one year prior to the LMP date or during pregnancy, where migraine is defined using combinations of ICD-10 diagnosis codes for migraine and/or NDC or HCPCS codes for acute migraine medication use (eg, triptans or ergots). Patients will be included if they meet at least one of the following criteria:
  - a. 1 migraine diagnosis claim from a "non-emergency" inpatient visit
  - b. 1 migraine diagnosis claim from an outpatient visit associated with a neurologist (variable STDPROV 260 in MarketScan CCE)
  - c. 1 migraine diagnosis claim from an emergency room visit
  - d. 1 outpatient migraine diagnosis claim **PLUS** 1 acute migraine drug (triptan or ergot-derivative) prescription claim within 180 days of each other
  - e. 2 outpatient migraine diagnosis claims between 7 and 180 days apart
  - f. 2 acute migraine drug (triptan or ergot-derivative) prescription claims between 7 and 180 days

Have complete medical and pharmacy benefits coverage for the twelve months prior to the LMP date through a commercial health plan.

- 3) Have continuous enrollment in the health plan from 365 days prior to the estimated date of conception through the end of pregnancy

Inclusion criteria for the cohort of live-born infants of pregnant women with migraine are as follows:

- 1) Live-born infants (based on a live delivery record) from the cohort of pregnant women with migraine. In the HIRD, the subscriber ID is unique for all family members, and infants with birth dates or enrollment records within 30 days of delivery will be matched. Mother-child linkage in the Marketscan CCE database will be determined using the following criteria:
  - a. Mother's ID (minus last 2 digits) Infant's ID (minus last 2 digits)
  - b. Mother's earliest delivery related claims date (year) from mother's claims records Infant birth year (from infant enrollment records). For mothers with delivery-related claims in December, infants with records in January of the following year will be included.
  - c. Infant's first enrollment date is not more than 180 days after mother's delivery related claims
- 2) Infants must be continuously enrolled for at least 90 days following birth which allows for the assessment of most major congenital birth defects

For comparator cohort A, we will include women who are exposed to other preventive medications during pregnancy as well as before LMP. When considering exposure to other preventive migraine medications before LMP, women will be included if exposure to these substances occurs within five of their half-lives prior to LMP.

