### Study Design Schema

[figure not shown]
Study design: Retrospective observational cohort study using data from MarketScan® Commercial Claims and Encounters databases and the HealthCore Integrated Research Database (HIRD)

Eligibility criteria for pregnant women with migraine: 1) Ages 16-44 years; 2) Evidence (diagnoses or acute medication use) of migraine prior to the last menstrual period (LMP); 3) Complete medical and pharmacy benefits; 4) Continuous health plan enrollment from 365 days prior to the LMP through the end of pregnancy

Eligibility criteria for live-born infants: 1) Infants from eligible pregnant women with migraine with record of live delivery and mother-infant linkage can be established; 2) Continuous enrollment for at least 90 days following birth

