#### **9.2.5 Study Follow-up**

The study will start in May 2019 and end in November 2027. Because this study uses secondary data that has already been collected, data for analysis will be included starting from May 2018 when erenumab-aooe was approved in the US. Women will be followed for pregnancy outcomes (spontaneous abortion or stillbirth) from their LMP date through the end of their pregnancy date, and all live-born infants will be followed for outcomes from birth (eg, small-for-gestational age) through the end of their first year (eg, major congenital malformations). Women with migraine or their infants will be censored when their enrollment in the database ends.

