When Z3A codes are not available, weeks of gestation for LMP estimation will be inferred using an algorithm that is informed by algorithms reported in the literature and refined clinical input will be utilized to estimate the corresponding EDC ([Hornbrook et al, 2007](#); [Margulis et al, 2013](#); [Margulis et al, 2015](#); [Mines et al, 2014](#); [Ailes et al, 2016](#)). The algorithms reported in the literature assume different lengths of gestation for the different pregnancy outcomes, such as full-term singleton births (40-39 weeks), multiples births (36-40 weeks), stillbirths (20-38 weeks), spontaneous abortions ( 20 weeks), and ectopic pregnancies (8 weeks). Recognizing these algorithms may over- or underestimate the true gestational age, other codes that indicate weeks of gestation (eg, HCPCS S2260, *induced abortion, 17-24 weeks*) or the trimester of pregnancy (eg, ICD-10 O09.612, *supervision of young primigravida, second trimester*) will be explored. For codes that are associated with a range of gestational age, an approximate mid-point of gestational weeks 4 days will be assigned based on the reported pregnancy-term code, eg, HCPCS S2260: *induced abortion, 17 to 24 weeks*, so the assigned GA is 20.5 weeks 4 days will be used for EDC estimation. Additional details on validation will be provided in the Statistical Analysis Plan (SAP) and the Medical Record Plan (MRP).

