### 9.6.2.2 Missing or Incomplete Data and Lost to Follow-up

The variables in this study will be measured by searching for diagnosis, procedure, and drug codes. Thus, the data will be captured to the extent that the MarketScan® CCE and the HIRD databases are appropriately populated with these codes. There will be no imputation of missing data. Covariates (eg, maternal race, alcohol use, smoking status) with extensive missing data will be described, but will not be included in regression models. The number of patients (women and infants) who are lost to follow-up when enrollment in the health plan ends will be described.

The use of medical records from HealthCore to confirm and validate the outcomes of interest as well as the timing of the pregnancy is a strength of this study; however, retrieval rates for requested medical records for mothers and/or infants will be less than 100%. We will provide a description of the patients who were excluded due to inability to obtain medical records and their characteristics based on the administrative claims. Additional discussion of the medical records procurement will be described in detail in the MRP.

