#### **9.8.1.2 Selection Bias**

The generation of mother-infant pairs is dependent on the infant being covered under the same insurer as the mother, and our mother-infant linkage algorithm could only link about 77% of live-born infants to their mothers (based on a completed exploratory analyses). The matched mothers were older (mean age 32.1 years) than the unmatched mothers (mean age 27.2 years), likely because younger mothers are

covered by their parents' health insurance. Other than age, the matched mothers were comparable to the unmatched mothers with regard to geographic region, gestational age, and occurrence of pharmacy dispensation during pregnancy.

The migraine case identification algorithm has not been validated in the MarketScan CCE database. Previously reported literature ([Kolodner et al, 2004](#)) and internal validation work in the Pharmetrics and Decision Resources Group claims linked with electronic health record databases showed that the algorithm has very high specificity but low sensitivity. Thus, it is possible that some migraine patients will be misclassified as non-migraine patients and will be excluded from this study. However, use of erenumab-aooe will not likely be missed as migraine diagnosis codes should appear in claims records due to its insurance coverage requirements.

Women will be followed through their pregnancy, and their live-born infants will be followed for one year after birth, or until the end of enrollment in the database. It is possible that we may miss outcomes if enrollment ends prior to the outcome. Differential loss to follow-up is a type of selection bias that poses a potential threat to the internal validity of any study. Loss to follow-up can be broadly conceptualized as any termination of treatment prior to the administrative end of the study, including, but not limited to, drop-out as a result of change in health plan, drop-out due to illness/frailty. For our study, we consider only health plan disenrollment. If all disenrollment occurred at random there would be loss in precision, but no increase in bias of the effect estimate. In most studies using claims data, we assume that health plan disenrollment does not occur at random. We will use sensitivity analysis to evaluate the potential impact of attrition bias.

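### Women who leave the health plan during pregnancy are excluded by eligibility, not censored as the follow-up text says, so their attrition is invisible and spontaneous abortions are retained more often than births

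*Protocol*

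**What the plan says.** Section 9.2.2.1 sets the enrolment criterion for women: "Have continuous enrollment in the health plan from 365 days prior to the estimated date of conception through the end of pregnancy". The Study Design Schema uses the same end point but starts the clock elsewhere: "Continuous health plan enrollment from 365 days prior to the LMP through the end of pregnancy". Pregnancy itself is identified through its ending, by a definition "which includes having evidence of at least one of the following pregnancy outcomes: spontaneous abortion, stillbirth, live birth, therapeutic abortion, or ectopic pregnancy". Section 9.3.1.1 then dates LMP backwards from that ending.

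Section 9.2.5 follows women for pregnancy outcomes "from their LMP date through the end of their pregnancy date" and adds: "Women with migraine or their infants will be censored when their enrollment in the database ends". The Abstract has the same rule. Section 9.6.2.2 promises: "The number of patients (women and infants) who are lost to follow-up when enrollment in the health plan ends will be described".

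Section 9.8.1.2 takes the threat seriously: "In most studies using claims data, we assume that health plan disenrollment does not occur at random". It goes on to promise a sensitivity analysis of attrition bias, and 9.8.4 repeats that outcomes may be missed if enrolment ends first. The enrolment analyses listed in 9.6.2.5.3 shorten the pre-LMP period to 180 days and examine infant non-linkage and infant disenrolment.

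**The concern.** For women, the follow-up span is the span over which eligibility already requires full enrolment. The two rules cannot both operate. A woman who leaves in mid-pregnancy is excluded, so nobody is left to censor, and a reported loss of zero women would say nothing about how many left.

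The exclusion also depends on the outcome. To be counted, a pregnancy must end while the woman is still enrolled. A pregnancy that ends early needs a short stay in the plan and one that ends at term needs a long one. Any steady disenrolment therefore keeps early losses more often than births. The proportion of pregnancies ending in spontaneous abortion is a deliverable even if no comparison is run, and 9.6.2.4.2 reports it as a simple proportion, which does not correct for this.

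**Working it through.** **The two rules together.** Women's follow-up runs from LMP to the end of pregnancy (9.2.5). Required enrolment covers that whole interval (9.2.2.1, Schema). So the number of eligible women censored before the end of pregnancy is 0, whatever the true attrition. The flow chart in 9.6.2.3.1 can show women with a recorded outcome and an enrolment gap. It cannot show women who left before any outcome claim, because they were never identified as pregnant.

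**Inputs for the size.**
- Spontaneous abortion: median 10.0 weeks by method 1, 13.1 by method 2 and 12.3 by method 3 (Table 1).
- Stillbirth: median 28.0 weeks by method 1 (Table 1).
- Full-term singleton birth: 39 to 40 weeks (9.3.1.1). I use 39.
- Ectopic pregnancy: 8 weeks (9.3.1.1).
- Live births: 62% of pregnancies in 9.5, and 75–80% in the Abstract.
- Assumptions, because the protocol gives no figure: constant disenrolment m of 1%, 2% or 3% per month, true spontaneous abortion 20%, true stillbirth 0.6%.

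The protocol states no figure of its own on this point to reproduce.

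**Retention.** The probability of staying enrolled w weeks after LMP is S(w) = (1 − m)^(12w/52).

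| m per month | S(10) | S(28) | S(39) | S(10)/S(39) |
|---|---|---|---|---|
| 1% | 0.977 | 0.937 | 0.914 | 1.07 |
| 2% | 0.954 | 0.878 | 0.834 | 1.14 |
| 3% | 0.932 | 0.821 | 0.760 | 1.23 |

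With spontaneous abortion at 13.1 weeks, the last column becomes 1.06, 1.13 and 1.20.

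**Observed spontaneous-abortion proportion** = 0.20 × S(10) / Σ p_k × S(w_k), for two mixes of the other outcomes.
- Mix A: the remaining 79.4% are term births (within the Abstract's 75–80%). At 3%: 0.1864 / (0.1864 + 0.006 × 0.821 + 0.794 × 0.760) = 0.1864 / 0.795 = 23.5%.
- Mix B: 62% term births (9.5), with the remaining 17.4% ending at 8 to 10 weeks (assumption). At 3%, with other endings at 10 weeks: 0.1864 / (0.1864 + 0.0049 + 0.62 × 0.760 + 0.174 × 0.932) = 0.1864 / 0.825 = 22.6%.

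| m per month | Mix A | Mix B |
|---|---|---|
| 1% | 21.1% | 20.8% |
| 2% | 22.2% | 21.7% |
| 3% | 23.5% | 22.5–22.6% |

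Dating spontaneous abortion at 13.1 weeks in mix B gives 20.7%, 21.4–21.5% and 22.2%. The direction does not change.

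**Stillbirth.** The relative change is S(28) / Σ p_k × S(w_k). In mix A it is 1.01, 1.02 and 1.03. In mix B it lies between 0.99 and 1.00.

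**Odds ratio, spontaneous abortion against term birth.** With monthly rates m1 and m2 in the two cohorts, a null odds ratio is multiplied by [(1 − m2)/(1 − m1)]^(12 × 29/52), where 29 = 39 − 10 weeks.
- Equal rates: 1.00.
- 2% against 1%: (0.99/0.98)^6.69 = 1.07.
- 3% against 1%: (0.99/0.97)^6.69 = 1.15, or 0.87 with the cohorts reversed.

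In mix B, with all other pregnancies as the reference, the last two factors fall to 1.05 and 1.11.

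**The case against.** The strongest reply is that the enrolment criterion is not the only cause. Pregnancy is identified from an outcome and LMP is dated back from it, so a woman who leaves first is unidentifiable under this method even without the criterion. That is true, and it means that deleting the criterion would not help. It does not rescue the censoring statement or the promised count.

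Second, the inputs are soft. The documents give no disenrolment rate, and nothing in them supports a threefold difference between cohorts. Table 1's 10 weeks is essentially an assigned value, and the first-line dating method is the Z3A codes. This stands, so the figures are a range under assumption and not an estimate.

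Third, 9.8.1.2 promises an attrition analysis without limiting it to infants, the bias analyses in 9.6.2.5.3 are open-ended, and detail is left to the SAP. This stands in part: an analysis of women's attrition may appear there. None of those listed in the protocol covers it, and the conflicting statements are fixed in the protocol itself.

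A reader might infer three stronger things that the documents do not support:
- That the reported spontaneous-abortion proportion will be too high on balance. Section 9.3.2.2 says stillbirth is more likely than spontaneous abortion to be medically attended, so unattended losses leave no claim and push the other way. Only the direction of this one mechanism is established.
- That all losses need only about 10 weeks of enrolment. Stillbirths need about 28.
- That the primary result is biased. The malformation proportion is taken among live births, so retaining losses more often than births does not distort it.

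**Conclusion.** The contradiction is certain and needs no assumption: women cannot be censored before their outcome, and the promised count of women lost will be zero whatever happens. The selection in favour of spontaneous abortion follows from any constant positive disenrolment rate. Its size rests on an assumed 1% to 3% per month, a true proportion of 20% and the outcome mix. Under these, 20% appears as about 21% at the low rate and 22.5–23.5% at the high rate. The stillbirth proportion moves by no more than about 3%, and the odds ratio is materially affected only if disenrolment differs between cohorts. This should be put right, but it concerns secondary outcomes and the reporting of attrition, not the primary comparison.

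**What to change.** 1. Correct the Abstract, 9.2.5 and 9.6.2.2 to say that women who disenrol before the end of pregnancy are excluded, not censored. In the same edit, reconcile the start of the enrolment period (estimated date of conception in 9.2.2.1, LMP in the Schema).
2. Report by cohort the number of women with pregnancy-care claims, such as Z3A or trimester codes, who disenrolled before any outcome. This makes attrition visible and shows whether it differs between cohorts.
3. Keep the unweighted analysis as primary. Add a sensitivity analysis of the spontaneous-abortion and stillbirth proportions and odds ratios that weights each completed pregnancy by 1/S(d), where S(d) is the probability of remaining enrolled for its duration d from LMP. Run it over a stated range of disenrolment rates, both equal and different by cohort.

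Weighting should not become primary. Cohorts are defined by claims relative to LMP and pregnancy, so non-pregnant women with migraine cannot supply a cohort-specific S(d), and 9.3.4 says that no validated dating method exists for non-live outcomes.

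The cost is a wording change and modest programming on enrolment data already held. The weighted results will have somewhat wider intervals and assume that disenrolment is independent of outcome within cohort.

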## **8. Research Question and Objectives**

### **8.1 Primary**

The primary objective is to estimate and compare the proportion of live-born infants with major congenital malformations among (1) women with migraine directly exposed to erenumab-aooe prior to and during pregnancy, (2) women with migraine exposed to other preventive migraine medications prior to or during pregnancy (comparator group A), and (3) women with migraine not exposed to erenumab-aooe or other preventive migraine medications prior to or during pregnancy (comparator group B). Comparative analyses will be undertaken if there is sufficient sample size and adequate distribution of covariates to adjust for confounding.

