The HIRD is a large administrative healthcare database maintained by HealthCore for use in health outcomes and pharmacoepidemiologic research. Health care utilization may be tracked for health plan members in the database back to January 2006. As of July 2019, there were 72.5 million unique individuals with medical coverage and more

than 51 million lives with both medical and pharmacy coverage. The HealthCore Integrated Research Environment (HIRE) has the ability to link the claims data in the HIRD to complementary data sources, including inpatient and outpatient medical records from healthcare providers submitting insurance claims, national vital statistics records, cancer and vaccine registries (state-by-state), disease and device registries, individual and provider surveys, point of care clinical data, and clinical oncology data.

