### 4. Other sensitivity analyses

We will also conduct sensitivity analyses limited to just the first pregnancy, and only among patients with no prior history of adverse pregnancy outcomes.

Patient characteristics and primary and secondary endpoints will also be described in any patients receiving erenumab who do not have a diagnosis for migraine in the chance of off-label use.

Analyses of major congenital malformations will also be conducted in all live born infants (not restricting to those with at least 90 days of follow-up) and limited to infants with at least a year of follow-up/enrollment after birth.

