**Appendix D. ICD-10-CM and CPT Procedure Codes to Identify Outcomes: Major Congenital Malformations\***

ICD-10-CM diagnosis or CPT procedure codes	Description of codes
	Central Nervous System
Q00.0-Q00.1	Anencephalus
Q05.0-Q05.9, Q07.01, Q07.03 w/o Q00.0 - Q00.1	Spina bifida without anencephalus
Q01.0 – Q01.9	Encephalocele
	Eye
Q11.0 – Q11.2	Anophthalmia / microphthalmia
	Ear
Q16.0, Q17.2	Anotia/microtia
	Cardiovascular
Q23.0	Aortic valve stenosis
Q21.1	Atrial septal defect
Q21.2	Atrioventricular septal defect (Endocardial cushion defect)
Q25.1	Coarctation of the aorta
Q20.0	Common truncus (truncus arteriosus or TA)
Q20.1	Double outlet right ventricle (DORV)
Q22.5	Ebstein anomaly
Q23.4	Hypoplastic left heart syndrome
Q25.2, Q25.4	Interrupted aortic arch (IAA)
Q22.0, Q22.1	Pulmonary valve atresia and stenosis
Q20.4	Single Ventricle
Q21.3	Tetralogy of Fallot (TOF)
Q26.2	Total anomalous pulmonary venous connection (TAPVC)
Q20.3, Q20.5	Transposition of the great arteries (TGA)
Q22.4	Tricuspid valve atresia and stenosis
Q21.0	Ventricular septal defect
	Orofacial
Q30.0	Choanal atresia
Q37.0 – Q37.9	Cleft lip with cleft palate
Q36.0 – Q36.9	Cleft lip alone (without cleft palate)
Q35.1 – Q35.9	Cleft palate alone (without cleft lip)
	Gastrointestinal
Q39.0 – Q39.4	Esophageal atresia/tracheoesophageal fistula
Q42.0 – Q42.9	Rectal and large intestinal atresia/stenosis
Q41.0 – Q41.9	Small intestinal atresia/stenosis

\* Using the core and recommended birth defects from the NBDPN list of birth defects descriptions ([https://www.nbdpn.org/docs/Appendix\\_3\\_1\\_BirthDefectsDescriptions2015\\_2016DEC14.pdf](https://www.nbdpn.org/docs/Appendix_3_1_BirthDefectsDescriptions2015_2016DEC14.pdf))

ICD-10-CM diagnosis or CPT procedure codes	Description of codes
	Genitourinary
Q64.10, Q64.19	Bladder exstrophy
Q64.12	Cloacal exstrophy
Q64.2	Congenital Posterior Urethral Valves
Q54.0 – Q54.9 (excluding Q54.4)	Hypospadias
Q60.0 – Q60.6	Renal agenesis/hypoplasia
	Musculoskeletal
Q66.0, Q66.89	Clubfoot
Q79.0, Q79.1	Diaphragmatic hernia
Q79.3	Gastroschisis
Q71.0 – Q71.9, Q72.0 – Q72.9, Q73.0 – Q73.8	Limb deficiencies (reduction defects)
Q79.2	Omphalocele

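### The 90-day enrolment rule for infants has no exception for death, so early deaths from a malformation drop out of the primary analysis

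*Protocol*

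**What the plan says.** The primary objective (section 8.1) is to "estimate and compare the proportion of live-born infants with major congenital malformations". That population is live-born infants, with no condition on survival.

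The infant inclusion criteria (section 9.2.2.1) narrow it: "Infants must be continuously enrolled for at least 90 days following birth which allows for the assessment of most major congenital birth defects". The Study Design Schema repeats the rule: "Continuous enrollment for at least 90 days following birth". Neither place mentions infants who die before day 90.

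The follow-up text does not fill the gap. Section 9.2.5 says "Women with migraine or their infants will be censored when their enrollment in the database ends", and section 9.8.1.2 says, on loss to follow-up, "For our study, we consider only health plan disenrollment". Death is not treated as a separate reason for short follow-up.

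Two sets of sensitivity analyses in section 9.6.2.5.3 bear on the rule. Item 4 repeats the malformation analysis "in all live born infants (not restricting to those with at least 90 days of follow-up") and again in infants with at least a year of enrolment. Item 2 looks at non-linkage and disenrolment at 30, 60 and 90 days, with detail left to the SAP.

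**The concern.** A minimum observation period is reasonable where it removes infants watched too briefly for a defect to be recorded. It is not reasonable for an infant whose defect was recorded at birth and who then died of it. That infant has the outcome and is removed because of it.

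Appendix D includes anencephalus, diaphragmatic hernia, renal agenesis and "Hypoplastic left heart syndrome". The protocol gives no mortality figures for these, but that some of them can be fatal within weeks is not in doubt. The cases most likely to be lost are the most severe.

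Two things are at stake. The proportions, which will be reported whether or not any comparison is run, are understated. If the drug raised the risk of lethal defects in particular, the comparison would also be pulled toward no effect, which is the wrong direction for a post-marketing safety study.

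**Working it through.** **Inputs from the protocol (section 9.5 and Table 2).** Background prevalence 3%, relative risk 2.00 (so 6% in the exposed), 1:4 matching, 80% power, 425 live births in the exposed group. Alpha is not stated there; two-sided 5% is assumed from the planned 95% confidence intervals.

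**Reproducing 425.** With p1 = 0.06, p0 = 0.03 and pooled p̄ = (0.06 + 4 × 0.03)/5 = 0.036:

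- n = [1.96·√(p̄(1−p̄)·1.25) + 0.842·√(p1(1−p1) + p0(1−p0)/4)]² / (p1−p0)²
- n = (0.4082 + 0.2124)² / 0.0009 ≈ 428, against 425 stated.
- Power at 425 is 79.8%.

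**Effect of the rule.** Let s be the share of malformed live-born infants who die before day 90 and so fail the criterion. The observed proportion is

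- q = p(1−s)/(1−p·s)

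The values of s are assumptions. Comparator s is set at 5%, so q0 = 0.03 × 0.95/(1 − 0.0015) = 2.85%. Power uses the same pooled formula.

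| Early death among exposed cases | q1 | Observed RR (q1/q0) | Power at 425 exposed |
|---|---|---|---|
| No loss in either group | 6.00% | 2.00 | 79.8% |
| 5% | 5.72% | 2.00 | 78% |
| 10% | 5.43% | 1.90 | 71% |
| 20% | 4.86% | 1.70 | 54% |

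**Equal loss in both groups.** For s = 2%, 5%, 10% and 20%, power at 425 is 79.1%, 78.0%, 76.2% and 72.0%, and the number needed rises from 428 to 436, 449, 472 and 526. The relative risk stays between 2.00 and 2.01. At s = 5% both proportions fall by about 5% in relative terms.

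**What the unequal rows imply.** The exposed group has 3 percentage points of background cases and 3 of excess. If background cases die early at 5%, an overall 10% means (0.06 × 0.10 − 0.03 × 0.05)/0.03 = 15% of the excess dies before day 90. An overall 20% means 35%.

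**A wider range for lethality of the excess**, with background loss at 5%: if 10%, 25%, 50% or 100% of the excess dies before day 90, the observed relative risk is 1.95, 1.80, 1.55 or 1.03, and power is 75%, 63%, 39% or 3%.

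**The case against.** The strongest reply is that the protocol already varies this restriction. The all-live-births analysis brings back early deaths that were linked to the mother, the one-year analysis varies it the other way, and item 2 of section 9.6.2.5.3 examines attrition. Comparing the sets is informative, so the question is partly which set should be primary. That is fair, but it does not remove the defect. The primary estimate is unchanged by any of these analyses. The unrestricted set mixes early deaths with infants who left the plan after days with little chance of a diagnosis, so a difference between the two results could not be attributed to either cause. The one-year set tightens the survival condition. None of them names death.

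The second reply concerns size, and much of it stands:

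- With equal early lethality, the ratio is essentially unbiased. The unequal rows assume that drug-related cases are three to seven times as lethal as background cases (15% or 35% against 5%), which nothing in the protocol supports or excludes.
- The outcome list also includes hypospadias, clubfoot, septal defects and clefts, so the overall early-death share may be low.
- 425 is a minimum. The protocol projects 1,400 to 1,500 exposed pregnancies in MarketScan. At 1,400 × 0.62 × 0.77 ≈ 668 infants, power is about 87% in the 10% row and 71% in the 20% row, before any loss to the 90-day rule or gain from pooling with the HIRD.
- A 5% relative fall in the proportions is small against precision. The comparator moves from 3.00% to 2.85% against a 95% half-width of about 0.8 points at 1,700 infants. The exposed group moves from 6.0% to 5.7% against about 2.3 points at 425.

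Finally, the mechanism needs an infant's enrolment to end at or soon after death, which the protocol does not state. It is the natural reading, since enrolment is the only follow-up measure used.

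**Conclusion.** The point holds. As written, the primary infant cohort is conditioned on surviving, enrolled, to day 90, while the objective concerns all live-born infants and the outcome can itself cause failure of the criterion. The direction for the proportions is downward. The comparison is biased toward no effect only if early lethality is higher among exposed cases.

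The amount cannot be derived from the protocol. Under the stated assumptions it ranges from almost nothing for the ratio (equal loss, 78% power at 5%) to a relative risk of 1.70 with 54% power at the minimum sample size. The unequal figures are adverse scenarios, not expectations. The criterion should be changed: the cost is small, and the present rule can hide the kind of harm the study is meant to detect.

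**What to change.** Reword infant inclusion criterion 2 in section 9.2.2.1, and the matching line in the Study Design Schema, along these lines: *90 days of continuous enrolment from birth, or continuous enrolment up to death if the infant dies before day 90*. Identify deaths from discharge status in claims where that field is available and, for the HIRD, from the linkage to "national vital statistics records" described in section 9.4. Keep the unrestricted and one-year sets as sensitivity analyses.

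The cost is one clause and one death flag, with three limits to state in the protocol:

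- Some early deaths will still look like disenrolment.
- Vital-statistics linkage is described only for the HIRD, so death capture may differ between the databases. Counts of infants admitted through the death clause should be shown by database before pooling.
- Infants who die before they are enrolled or linked to the mother remain missing.

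With incomplete capture, the revised rule still recovers some cases that the current one drops.
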